B. A lay health advisor (LHA) will be recruited from the community to provide counsel about EOL care to patients who will receive the intervention. The LHA will undergo training in how to provide culturally sensitive EOL care for AAs via the APPEAL (A Progressive Palliative Care Educational Curriculum for the Care of AAs at Life's End) Curriculum created at Duke University, the Respecting Choices® Advance Care Planning curriculum, or other appropriate training program depending on availability. After training, the LHA will participate in in-service work with the Parkland Palliative Care Team and the PI.

Aim 2:

We will use the e-EOL algorithm (IRB #: STU 122010-078) to identify AA patients hospitalized at Parkland who have advanced breast, lung, and colorectal cancer to identify potentially eligible candidates for the intervention (See Aim 1 eligibility criteria); however, if sufficient numbers are not identified, patients with other advanced cancers will also be considered. Once eligibility is confirmed the PI or her designee (research assistant, coordinator, or LHA) will introduce the study to the patient, and obtain informed consent. Each patient will be asked to identify a primary caregiver who may be able to participate in the intervention. Of note, if a caregiver cannot be identified, is not eligible, or cannot participate in the intervention for other reasons (scheduling difficulties, etc.), the patient will still be allowed to participate. Caregivers are not required to participate in the intervention (i.e. watch the DVD segments), though it will be encouraged. The PI or her designee (research assistant, coordinator, or LHA) will contact the patient to confirm participation in the study, and arrange a time to meet to conduct the intervention. We anticipate that 48 patients (and their caregivers if available) will be enrolled in the study (16 for each type of cancer). We plan to conduct a small, pilot randomized controlled trial with up to 24 patients (and their caregivers if available) in the intervention arm, and up to 24 patients (and their caregivers if available) in a usual-care control group. The PI will randomize every other eligible patient (and caregiver if available) to the usual-care control group.

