The PI or her designee will conduct a pre-assessment interview with eligible patients to assess their knowledge of advance care planning, hospice, and palliative care. The PI or her designee will also attempt to contact identified caregivers to conduct an assessment of caregivers' knowledge of their loved one's prognosis, perceived quality of life, treatment plan, physical symptoms, and preferences for aggressive treatment. Verbal consent will be obtained, and caregivers will be given the option of completing the interview in person or by phone. The LHA will conduct an in-hospital visit with patients (and their caregivers if available) randomized to the pilot intervention. During this visit, the LHA will assist them in watching the EOL care DVD segments. If a patient's caregiver is unable to be present for viewing, they will be given the option of watching the video via a password protected website. Afterward, the LHA will answer questions and provide additional information as needed. The LHA will then use counseling scripts created by the PI and research team to probe in more depth about the patient's goals of care, understanding of their clinical condition, prognosis, and treatment options, mistrust and spirituality, decisional conflict, quality of life and healthcare utilization. All participants will be asked about their intent to consider EOL care options, and their stage of decision-making will be noted (pre-contemplation, contemplation, preparation, or action). The LHA will tailor the discussion to the patient's values, preferences, concerns, and clinical circumstances. Those who express interest in hearing more about EOL care options will be encouraged to discuss this with their doctor. The LHA will offer to update their attending physician on the discussion and help communicate the patient's desire for a palliative care consult or advance directive if applicable. Specific questions about prognosis will be referred to the treating physician. Formal palliative care consults will be ordered and performed in the usual fashion if requested. This visit will be no more than 2 hours in length. A follow-up visit will also be conducted to address any questions that participants may have with regard to the study.

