9. Recruitment Methods and Consenting Process: Aim 1: The PI and research assistant will work with the attending physicians in the Parkland Palliative Care Clinic, Amelia Court Geriatrics Clinic, the Parkland inpatient Geriatrics and General Internal Medicine services, and researchers at the Simons Cancer Center to identify eligible candidates for semi-structured interviews and focus groups. Information will also be obtained for patient's caregivers, and they will be contacted by phone and regular mail to assess their interest in participation.

Palliative Care providers will be recruited via professional contacts. Providers will be approached via email and phone to assess their interest in participating in the focus group.

AA Religious leaders will be recruited from the African American Pastors Coalition and/or local AA churches. They will be approached by email (if available) and phone to assess their interest in participating in the study.

Aim 2: Patient participants will be recruited via development of a computerized algorithm using EMR data to identify hospitalized patients with advanced illness appropriate for EOL care discussion according to national guidelines. Development and validation of this algorithm is currently in process and has already received IRB approval (STU 122010-078: Evaluation of Racial Differences in Palliative and End-of-Life Care among Persons with Life-Limiting Illness). The algorithm will run once every day to flag potentially eligible candidates using an IT protocol used successfully in previous research at Parkland. The PI or her designee (research assistant or research coordinator) will contact the attending physicians of those identified by the algorithm to confirm eligibility and get permission to introduce the study to those patients. Creation of the algorithm is actually Aim 1 of an AHRQ-funded study that includes all three aims; consequently, the algorithm will be complete enough to use for recruitment in Aim 2 described here.

The PI or her designee (research assistant, research coordinator, or LHA) will contact each patient's primary caregiver by phone to confirm their participation in the study.

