The PI will be responsible for all recruitment. Verbal informed consent will be obtained from all study participants. The PI, Co-Investigators, and study personnel will be authorized to obtain informed consent from participants. Waiver of documentation of informed consent can be justified because the research presents no more than minimal risk to subjects—study participation is limited to responding to survey questions—and because the research involves procedures for which written consent is not normally required outside the research context. Participants will be informed that they do not have to participate and can stop their participation at any time.

10. Potential Risks: Risks associated with this research include a potential minimal risk of loss of confidentiality. Every effort will be made to keep patient information confidential as described below. Some of the questions could be upsetting to patients, as these questions probe the patients' knowledge of their diagnosis and level of spirituality. Additional risk includes psychosocial concerns such as anxiety. Should the LHA encounter a patient who has an unexpected reaction or becomes upset during the interview, the PI (a physician trained in geriatrics, hospice, and palliative medicine) will be contacted to assist. Additionally, pastoral care, psychiatry, and psychology services will be made available to participants should they desire it. Patients will have access to the inpatient consult services and outpatient follow-up should the need arise. There are no questions that would pose a risk to the patients' reputations, residency status, or employment.

11. Subject Safety and Data Monitoring: This is a minimal risk protocol involving only the potential risk of loss of confidentiality. All medical and other identifying information will be kept in a secure location, only accessible to the PI and/or her designee. Processes to maintain data integrity will be followed. After data collection is completed, all patients will be assigned a unique identifier, all data will be de-identified, and no protected health information will be stored. The database will be stored on a secure server with access limited to the research team. Interview forms will be locked in a secure location with access provided only to the research team. All computers used for this project will be password protected.

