The PI will use descriptive statistics to characterize study participants and proportion of intervention elements and follow-up assessments completed. The specificity and positive predictive value of the e-EOL algorithm operating in real world practice will be assessed using methods described for Aim 1 with physician chart review as the criterion standard. Acceptability and feasibility process data will be tallied. The main decision making outcome will be *change in the stage of intent to discuss EOL care options* from baseline through all follow-up intervals. Movement to an adjacent stage is a 1 point change. The PI will assess several aspects of stage change based on the proportion of patients at each time interval showing: 1) *any stage pro/regression*, and 2) *full progression to the action stage of discussion EOL care options*. Mean and range of progression at each interval will also be reported. The proportions above and means for *persistent change* will also be defined as the difference between baseline and 6 months (or 3 months if no 6 month contact or patient deceased). The PI will similarly examine pre- and post-intervention changes over time in knowledge, attitudes, and beliefs about EOL care and prognosis, decisional conflict, and QOL using non-parametric tests among the intervention group versus controls. Pre-specified subgroup analyses will stratify change in outcomes by: condition, mistrust, and spirituality. To achieve sensitivity of around 50% (with 10% confidence intervals, e.g. CI: 40% to 60%) in the outpatient algorithm, the PI will need to review 150 charts of patients diagnosed with metastatic (Stage III or IV) breast, lung and colorectal cancer (75 "test positive" and 75 "test negative" cases). The controlled pilot study in Aim 3 is designed to establish: feasibility, acceptability, detect preliminary efficacy signals (changes in behavioral intent, knowledge, attitudes, beliefs, decisional conflict), and generate point/variance estimates to be used to in power calculations for a future fully-powered RCT. The PI proposes a small pilot RCT that will include 24 patient-caregiver pairs in each arm (intervention versus a usual care control group). This will yield greater than 80% power to detect a large intervention effect defined as an absolute difference in desired primary outcome of 40% (across a range of different point estimates), and between 60-70% power to detect a more modest absolute difference of 30% between the two groups (across a range of point estimates). To ensure the ability to recruit the additional patient-caregiver pairs for the study, the PI will extend the enrollment period from 15 months to 18 months. Parkland Hospital providers care for more than 900 breast, lung and colon cancer patients per year, and roughly 40% are African American; consequently the PI believes that she will be able to successfully enroll this number of participants within an 18-month timeframe.

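### The pilot is labelled randomized, but arms are assigned by alternation under the PI who also runs recruitment, so the next arm is always known and the comparison is open to selection bias

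*Combined protocol and SAP*

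**What the plan says.** **Allocation.** Section 3 (Concise Summary of Project, Aim 2) describes the design this way: "We plan to conduct a small, pilot randomized controlled trial with up to 24 patients" in the intervention arm and the same number in usual care. The allocation rule is: "The PI will randomize every other eligible patient (and caregiver if available) to the usual-care control group". Section 4 (Study Procedures, For Aim 2) and the Statistical Analysis Plan repeat the randomized label without adding a mechanism.

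**Recruitment and consent.**
- Section 9 (Recruitment Methods and Consenting Process): "The PI will be responsible for all recruitment".
- Section 9: an algorithm flags candidates daily. The PI or a designee then contacts the attending physician "to confirm eligibility and get permission to introduce the study to those patients".
- Section 3, Aim 2: "the PI or her designee (research assistant, coordinator, or LHA) will introduce the study to the patient, and obtain informed consent". The lay health advisor (LHA), who delivers the intervention, is therefore among those who may take consent.
- Section 9: "The PI, Co-Investigators, and study personnel will be authorized to obtain informed consent from participants".
- Section 4, Aim 2: "The PI or her designee will conduct a pre-assessment interview with eligible patients".

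**Use of the arms.** The SAP compares stage change in intent, and examines knowledge, beliefs, decisional conflict and quality of life "using non-parametric tests among the intervention group versus controls". It also assigns the pilot the tasks of detecting early efficacy signals and supplying point and variance estimates for the power calculation of a future full-size trial.

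**The concern.** Alternation has no random element. Once one patient's arm is known, so is every later one. Here the person who assigns the arms also answers for recruitment, and the staff who approach patients, take consent and do the baseline interview are not described as unaware of the sequence.

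This matters more than usual because of the outcome. The decision-making endpoint is movement through stages of intent to discuss end-of-life care, and openness to that conversation can be sensed at the bedside. A recruiter who knows that the next slot is intervention can, without any bad intent, approach a receptive patient sooner, press consent harder, or wait a day. The arms then differ at entry in their propensity to progress, and that difference cannot be separated from the intervention effect. Using change from baseline does not remove it, since two patients at the same stage can differ in how likely they are to move.

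At stake are the between-arm comparison, the effect estimate passed to the next trial, and the accuracy of the word randomized in any report.

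**Working it through.** **1. The plan's own figure.** The SAP claims more than 80% power for a 40-point difference with 24 per arm. It states neither alpha nor sidedness; I assume 5% two-sided.

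Power = Φ{[d − 1.96·√(2p̄(1−p̄)/24)] / √([p₁(1−p₁)+p₂(1−p₂)]/24)}

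Worst case, 30% v 70%: [0.40 − 1.96 × 0.1443] / 0.1323 = 0.885, so power is 81.2%. Over control rates from 5% to 55% it runs from 81.2% to 91.9%, so the claim reproduces. For 30 points the formula gives 54.9% to 75.4%, so the stated 60–70% reproduces only in part. Nothing below depends on this. Concealed 1:1 allocation at the same size leaves nominal power unchanged.

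**2. Search for a random or concealed step.** I looked for sequence generation, concealment, an independent allocator and assessor blinding in sections 1 to 13 and the SAP. None is described. The allocation sentence is complete, so this is not a redaction or a text-extraction gap.

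**3. Predictability over 48 assignments.** For blocks, the recruiter guesses the arm with more slots left or, if block sizes are unknown, the arm that is behind.

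| Method | Correct guesses of 48 |
|---|---|
| Alternation, starting arm unknown | 47 certain (98%) |
| Alternation, starting arm known | 48 (100%) |
| Permuted blocks of 4, size known | 34.0 (71%) |
| Permuted blocks of 6, size known | 32.8 (68%) |
| Permuted blocks of 8, size known | 32.0 (67%) |
| Blocks of 4 or 6 at random, three strata of 16 | 32.8 (68%) |
| Simple randomization | 24 (50%) |

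The block rows are simulated. They assume that past assignments are visible, as they would be in an open study.

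**4. What an entry imbalance does to the test.** Assume no intervention effect, but chances of progression p₁ and p₂ that differ because of selective entry. The exact rejection probability is the sum, over all pairs (x, y) that reject at two-sided 5%, of Bin(x; 24, p₁) × Bin(y; 24, p₂).

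| Intervention v control | Chi-square, uncorrected | Fisher |
|---|---|---|
| 50% v 50% (no imbalance) | 6.0% | 2.9% |
| 55% v 45% | 12.2% | 7.0% |
| 60% v 40% | 31.2% | 21.5% |
| 40% v 20% | 33.3% | 23.6% |

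The last row shows that the result does not hinge on centring at 50%. The normal approximation, with rates centred on 20% to 40%, gives a chance of significance favouring the intervention of about 10–14% for a 10-point imbalance and 29–41% for 20 points, against a nominal 2.5%.

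**5. Effect on the estimate.** With no true effect, a 20-point entry imbalance appears as a 20-point effect: half of the 40 points the SAP calls large, and two thirds of the 30 points it calls more modest.

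**The case against.** - **It is a pilot.** Its primary process outcome is feasibility and acceptability, and completion counts depend little on concealment. This stands for those outcomes. It does not cover the comparison of arms, the efficacy signals or the inputs to the next trial, all of which the SAP plans.
- **Staff do not choose freely.** An automated flag and the attending physician's permission come before any approach. This narrows who can be approached, but it does not hide the next arm, and timing, order and persuasion remain discretionary.
- **The rule alternates eligible patients.** If the sequence advances with each confirmed-eligible patient, skipping one does not change the next one's arm. That is a fair reading, and the text does not settle when assignment occurs. Under it, bias enters through differential approach or consent instead. If assignment precedes consent, that route is wide open.
- **The direction is uncertain.** Patients already near the action stage have less room to progress, so enrolling ready patients in the intervention arm could bias the result either way. This stands. The table shows one direction only, and the estimate is unreliable in both.
- **The illustration is assumed.** The splits have no source in the documents, and the SAP names neither chi-square nor Fisher for stage change. Both are true; the figures show sensitivity, not an expected size.
- **The 50% comparator.** It fits simple randomization only. Under blocking the fair contrast is 98–100% against roughly 67–71%, which is still large.

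**Conclusion.** The concern holds, and the allocation rule must be changed. As written it is deterministic, it is operated by the person responsible for recruitment, and it has no concealment. The study is therefore not a randomized trial, whatever it is called. At least 47 of 48 assignments are known in advance; that follows from the text and rests only on the enrolment target of 48. The size of any resulting bias cannot be derived from the documents. On the assumed 10- and 20-point imbalances around 50%, the false-positive rate rises from 6.0% to 12.2% and 31.2% with chi-square, or from 2.9% to 7.0% and 21.5% with Fisher. Feasibility and acceptability are much less affected. No analysis can restore concealment afterwards, so this has to be put right before enrolment or disclosed after it.

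**What to change.** Replace the allocation sentence in section 3, Aim 2 with wording such as:

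> After consent and completion of the baseline interview, each patient (with any participating caregiver) is allocated 1:1 to intervention or usual care from a computer-generated list in randomly permuted blocks of varying, undisclosed size. The list is prepared and held by someone not involved in recruitment, consent or delivery of the intervention, and is released one assignment at a time through sequentially numbered opaque envelopes or a database module.

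Refer to this paragraph from section 4 and the SAP, so that the randomized label rests on a stated method. The wording also settles whether assignment comes before or after consent.

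Stratification by cancer type is optional. If it is used, a stratum for other advanced cancers is needed, because sections 3 and 6 allow them. Without strata, a list of six blocks of 4 and four blocks of 6, in random order, gives 6 × 4 + 4 × 6 = 48 and keeps 24 per arm.

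If patients have already been allocated by alternation, describe the study as quasi-randomized, report the procedure actually used, and attach that caveat to any estimate carried into the future trial.

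Cost: a one-paragraph amendment, a list generated once, and an independent holder with envelopes or a database module. That is a small new procedure. No extra patients are needed and nominal power is unchanged.

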The LHA will meet with eligible patients and available caregivers in the intervention arm and assist them in watching the developed DVD segments. Afterward, the LHA will answer questions and provide additional information. They will tailor the discussion to the patient's values, preferences, concerns, and clinical circumstances. The patients who are enrolled in the usual care arm will not receive the intervention.

The primary process outcome tested will be the feasibility and acceptability of the intervention. Feasibility success will be measured by the number and rates of patients/caregivers who complete the intervention and follow-up interviews. The primary decision-making outcome is change in intent to discuss EOL care options based on the Transtheoretical Stages of Change Model (i.e., pre-contemplation, contemplation, preparation, and action). Secondary outcomes measured will include: 1) knowledge of prognosis and EOL care options; 2) quality of life, which will be measured by the McGill QOL Questionnaire, a well-validated 20 item scale developed to measure quality of life at the end of life; 3) health care utilization, such as outpatient visits, ER visits, hospitalizations, use of hospice services; and 4) date and place of death if applicable. Other patient and treatment variables will also be collected. The study variables, data sources, time frame of measurement, and references for the validated instruments are outlined in Table 2.

Table 2. Study Variables, Data Sources, and Time Frame Measurements

Variable	Source	Index Admit	Time Frame		
			1 month	3 months	6 months
Sociodemographics, clinical, treatment data	Chart review	X			
Knowledge of prognosis, EOL care options	Interview	X	X	X	
Feasibility and acceptability of the intervention	Interview	X	X	X	
Mistrust and spirituality	Interview	X	X	X	
Intent to consider EOL care options	Interview	X	X	X	X
Quality of life	Interview	X	X	X	
Healthcare and EOL utilization	Interview, chart	X	X	X	X

4. Study Procedures:

For Aim 1:

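### The procedures do not secure a pre-intervention baseline for stage of intent, and the planned between-arm comparison of decisional conflict has no described control data

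*Combined protocol and SAP*

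**What the plan says.** **Stage of intent.** Section 3 (Aim 2) states: "The primary decision-making outcome is change in intent to discuss EOL care options". The Statistical Analysis Plan measures it "from baseline through all follow-up intervals", scores it by the rule "Movement to an adjacent stage is a 1 point change", and defines persistent change against baseline too. The SAP will also "similarly examine pre- and post-intervention changes over time in knowledge, attitudes, and beliefs about EOL care and prognosis, decisional conflict, and QOL", comparing intervention with control by non-parametric tests. A pre-intervention value is therefore intended.

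Section 4 (For Aim 2) describes a "pre-assessment interview with eligible patients to assess their knowledge of advance care planning, hospice, and palliative care". It then describes the lay health advisor (LHA) visit, which is for patients randomized to the intervention: DVD viewing, questions and answers, then scripts that probe several topics, including "mistrust and spirituality, decisional conflict, quality of life and healthcare utilization". The next sentence reads: "All participants will be asked about their intent to consider EOL care options, and their stage of decision-making will be noted".

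Section 3 says of the schedule: "The study variables, data sources, time frame of measurement, and references for the validated instruments are outlined in Table 2". Table 2 marks intent at Index Admit and at 1, 3 and 6 months. Mistrust and spirituality, and quality of life, are marked at Index Admit and at 1 and 3 months. The Index Admit column is not divided into before and after the LHA visit.

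**Decisional conflict.** It is named once in section 4, in the script topics above, and twice in the SAP: in the between-arm comparison and in the list of preliminary efficacy signals.

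**The concern.** A change score is only as sound as its starting value. Controls see no DVD and receive no LHA counselling, so their index reading is unexposed whenever it is taken. An intervention patient's reading could come after the session meant to move it. The error would then fall on one arm only, and randomization does not repair that. It would tend to understate the between-arm difference, and it would pass into the point and variance estimates that the pilot is meant to supply for the later full trial.

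The SAP's subgroups by mistrust and spirituality are exposed in the same way. The SAP does not say which measurement defines the strata, and the scripts probe both topics after the DVD.

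Decisional conflict raises a simpler problem: an analysis is promised for which no control data, no pre-intervention data and no follow-up data are described.

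**Working it through.** **1. Where stage of intent is placed at the index admission**

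| Place | What it gives | Fixes the reading before the DVD? |
|---|---|---|
| SAP | Change from baseline; parallel measures described as pre and post | Intended, but no time point given |
| Section 4, patient pre-assessment | Knowledge only | No; intent is not listed |
| Section 4, LHA visit text | Stage noted, in a sentence that follows the DVD, questions and scripts | No; the order suggests after |
| Table 2 | Intent marked at Index Admit, one column | No; the LHA visit is in the same hospital stay |

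The stage sentence covers all participants, whereas the LHA visit is for the intervention arm only. Controls are therefore probably asked, and a pre-DVD reading is possible. It is not stated.

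**2. Where decisional conflict is measured**

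| Place | Mentions |
|---|---|
| Table 2 (7 rows) | 0 |
| Section 3 secondary outcomes (4) | 0 |
| Section 4 patient pre-assessment | 0 |
| Section 4 follow-up interview topics (6) | 0 |
| Section 4 LHA scripts, intervention arm, after the DVD | 1 |
| SAP | 2 |

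The follow-up interviews ask similar questions about the outcomes in Table 2, which omits it.

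**3. Effect on the score.** There are four stages and adjacent stages differ by 1 point. A patient who moves k stages before recording has a measured change equal to the true change minus k, with k at most 4 − 1 = 3.

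**4. The plan's own power figures.** With 24 per arm, the SAP claims more than 80% power for a 40-point difference and 60–70% for 30 points. It states no alpha, sidedness, test or control rate. I assumed alpha 0.05, no dropout, and control rates of 10–50% (40 points) or 10–60% (30 points).

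| Test | 40 points | 30 points |
|---|---|---|
| One-sided Fisher | 83.6–89.7% | 58.9–71.1% |
| Two-sided pooled z | 81.2–88.1% | 54.9–68.0% |
| Two-sided Fisher | 75.0–83.4% | 47.0–60.2% |

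One-sided Fisher reproduces both claims to within about 1 point. The power statement is not in dispute here.

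**5. Illustration of attenuation.** Assumptions, none from the documents except the 40-point difference and 24 per arm: 80% of intervention patients and 40% of controls truly progress; a share s of the difference occurs before stage is recorded; those patients do not move again.

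- Measured intervention rate = 0.80 − 0.40s.
- Measured difference = 0.40(1 − s).
- Power = the sum, over all pairs of counts, of Bin(i; 24, intervention rate) × Bin(j; 24, 0.40) wherever the two-sided 0.05 test rejects.

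| s | Measured rates | Difference | Pearson chi-square | Fisher |
|---|---|---|---|---|
| 0 | 0.80 vs 0.40 | 40 points | 84.4% | 76.0% |
| 0.25 | 0.70 vs 0.40 | 30 points | 59.0% | 47.1% |
| 0.50 | 0.60 vs 0.40 | 20 points | 31.2% | 21.5% |
| 0.75 | 0.50 vs 0.40 | 10 points | 12.0% | 7.0% |

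Other control rates show the same pattern. With the two-sided pooled z test, shares of 0, 25, 50 and 75% give 88, 68, 41 and 16% at a control rate of 10%, and 81, 55, 29 and 11% at 30%.

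**The case against.** The best reply is that a baseline is plainly planned. Table 2 schedules intent by interview at Index Admit. Knowledge sits in the same column with the same source, and section 4 puts knowledge in the pre-assessment, so the index interview may simply be the pre-assessment. Nor is section 4 strictly chronological: consent, for instance, is mentioned after the interviews. A sentence about all participants cannot be only a step in a visit that controls do not have. On this view the harm is conditional, the illustration rests on the reviewer's own rates, and the assumption of no further movement is the worst case. Feasibility and acceptability are the primary process outcome, and efficacy is only a preliminary signal.

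Much of this is fair. It shows that a pre-intervention reading is intended and possible, and that a post-exposure baseline has not been demonstrated. The power table carries no evidential weight beyond showing direction and sensitivity. One SAP measure may also escape: full progression to action would not depend on baseline timing if it means being in the action stage at follow-up.

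The reply does not show that the procedures place the reading before the DVD. The shared column does not settle it either, because it also holds acceptability of the intervention, which cannot be wholly pre-intervention.

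On decisional conflict, the reply can say only that it is not among the listed outcomes and that the outcome list is open-ended. That limits the consequence but supplies no control measurement.

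**Conclusion.** Both parts hold.

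- **Stage of intent:** the timing of the baseline is left open, and the only narrative order given would make it post-exposure in the intervention arm alone. The likely direction is an understated effect. The size is unknown: 1 point per stage moved before recording, at most 3 per patient. The percentages in the illustration depend wholly on its assumed rates and shares.
- **Decisional conflict:** this rests on the text alone. The between-arm comparison of change cannot be run from the data collection described.

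This should be fixed before enrolment. It affects the main decision-making outcome and the estimates meant for the next trial, but it does not affect the tallying of feasibility.

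**What to change.** 1. **Section 4 (For Aim 2):** state that stage of intent, mistrust, spirituality and quality of life are collected from patients in both arms at the pre-assessment interview, before allocation and before any DVD viewing or LHA counselling. The limit should be counselling rather than contact, because section 3 lets the LHA introduce the study and confirm participation.
2. **SAP:** define that value as the baseline for all change scores and for the mistrust and spirituality subgroups.
3. **Table 2:** label the Index Admit entry for these items as pre-intervention baseline. The acceptability row needs its own timing, so split the column or add a footnote.
4. **Decisional conflict:** either name an instrument and add it to that baseline and to the follow-up interviews in both arms, with a row in Table 2, or delete it from the SAP comparison and the efficacy-signal list.

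The cost is a somewhat longer pre-assessment interview and no new staff. Apart from decisional conflict, the items are already scheduled at the index admission, so the change mainly fixes their timing. Deleting decisional conflict costs nothing.
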